## INTRODUCTION

Anterior knee pain (AKP) remains a common cause of persistent pain after total knee arthroplasty (TKA). The reported incidence varies from 8% to more than 50%, and it has a negative effect on patient quality of life and satisfaction. Many factors may contribute to AKP, but there is no clear consensus with regard to its etiology and treatment.

Lateral retinacular release (LRR) has been proposed as a surgical option to prevent AKP syndrome. This is based on the fact that excessive lateral patellofemoral pressure due to a tight lateral retinaculum contributes to patellofemoral disorders like AKP, patellar chondral lesions, or patellofemoral osteoarthritis. Some authors suggested that the origin of AKP can be found in the degenerative neuropathy seen in the lateral retinaculum of symptomatic patients. Therefore, its release would improve this pain by denervating the tissue.

Accordingly, the mechanism by which lateral release relieves pain may be the reduction of lateral tension decreasing the surface pressure, as well as the denervation of the retinaculum.

With TKA, forces and peak pressures significantly increase in the patellofemoral joint. For that reason, some authors are keen advocates of the lateral release with the intent to ease AKP. They perform it systematically even if the tracking is correct. A clinical randomized trial suggested that routine LRR can reduce AKP in TKA without patellar resurfacing.

### Objectives and hypothesis

The primary objective of this prospective randomized double-blind trial is to evaluate the effect of LRR on AKP after TKA with patellar replacement when compared to the resurfaced patella without release.

The secondary objectives are to assess and compare the functional and radiological outcomes between the groups after 12 months.

The hypothesis is that LRR would decrease the incidence of AKP after TKA with patellar resurfacing, as well as it would improve functional outcomes.

## MATERIALS AND METHODS

### Study design and eligibility criteria

A prospective, randomized, and double-blinded clinical trial is designed. All the patients that will undergo a primary TKA in our center from October 2019 through December 2020 are included.

The inclusion criteria are patients aged 40-90 years with a diagnosis of knee osteoarthritis who signed written informed consent.

The exclusion criteria are patients with a prior major surgery on the same knee (high tibial or distal femoral osteotomy, patellar realignment), important preoperative malalignment

(varus or valgus  $>15^\circ$  or flexion deformity  $>15^\circ$ ), and an inability to sign informed consent.

The study was approved by the Research Ethics Committee of our institution (2019/8993/I).

A total of 220 patients are randomized into either the LRR group (Group A) or non-release group (Group B).

### **Surgical procedure**

Computer-generated randomization sequencing will be conducted before the surgery.

All the procedures will be performed by five experienced surgeons from the knee unit of our institution, using a midline anterior approach and a medial parapatellar arthrotomy. An extramedullary guide will be used for tibial cutting and intramedullary guide for femoral cutting, following mechanical alignment technique. The prosthetic components will be implanted in a one-stage cementing technique after standard bone cuts. The patella is going to be always replaced with a symmetric implant.

In the release group (Group A), a retinacular release will be performed 2cm lateral to the lateral margin of the patella.

[figure not shown]
The postoperative rehabilitation protocol will be the standardized for every total knee arthroplasty in our hospital.

### **Data collection and outcome measures**

Preoperatively, demographic data regarding age, gender, body mass index and laterality will be recorded. At the preoperative visit and at the 1-year follow up, the following clinical and radiological data will be collected by an examiner blinded to the surgical technique performed:

[figure not shown]
- Patellar pain and function are evaluated with the patellofemoral score designed by Feller et al. The score is distributed with a maximum of 15 points for the intensity of anterior knee pain, 5 points for quadriceps strength, 5 points for the ability to rise from a chair and 5 points for stair-climbing ability.
- The Knee Society Score (KSS) for both the Knee and the Function scores, 0 being the worst and 100 the best possible result in each section.
- The pressure pain threshold (PPT) determined using pressure algometry (PA). The PPT is assessed 3 times in each knee, with a calibrated electronic algometer (Algometer, Somedic Sales, Hörby, Sweden) with a  $1\text{cm}^2$  probe placed perpendicular to the skin in the center of the anterior aspect of patella. The evaluator increases the pressure 20 kPa/s until the sensation become painful and the patient says “stop”. The final PPT value taken is the average of the 3 measurements.
- The Visual Analogue Scale (VAS) referred by the patients at rest, when walking and when going up and downstairs.

- Patellar height. Measured in the lateral view using the Caton-Deschamps index and its application in TKA.

**Figure 1.** Patellar height measurement defined as the ratio of the length of the patellar articular surface (B) and the distance between the lower pole of patellar articular surface and the anterior border of the tibial plateau (A) preoperatively or the tibial component surface postoperatively (A').

- Patellar tilt. Defined in the axial view, as the angle subtended by the anterior intercondylar line and the equatorial line of the patella preoperatively or a line drawn through the prosthesis-bone interface postoperatively.

**Figure 2.** Patellar tilt measurement.

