### Statistical analysis

The sample size calculation of 110 patients in each group was based on assuming a minimum difference of 1 point in the VAS value with a standard deviation of 2.5. A probability level of 0.05, a power of 80% and a drop-out rate of 10% were assumed.

Descriptive statistics were used for the demographic data. Continuous variables and measured scores were presented as mean and standard deviations and categorical variables as number and percentage. Between group comparisons were evaluated with the Mann-Whitney U test. These comparisons were performed with the preoperative and postoperative measurements. Differences between the groups in terms of changes or improvements (post vs. pre) were also assessed with the Mann-Whitney U test.

STATA version 15.1 (StataCorp, College Station, TX, USA) was used for the statistical analysis with p values of 0.05 being considered statistically significant.

For the calculation of intraclass correlation coefficients (ICC) two-way random-effects model approximation was performed, being in terms of *Shrout and Fleiss* notation ICC(2,1) for intrarater agreement and ICC(2,2) for interrater agreement.

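### Pressure pain threshold (PPT) is collected before surgery and at 1 year but compared only by unadjusted rank tests, so the baseline reading, and any contralateral one, is used inefficiently

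*Combined protocol and SAP*

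**What the plan says.** Under Data collection and outcome measures, the clinical measures are taken "At the preoperative visit and at the 1-year follow up". For PPT, "The PPT is assessed 3 times in each knee", and "The final PPT value taken is the average of the 3 measurements". The section does not name a contralateral or non-operated knee, and it does not say which knee's value goes into the group comparison. Side of surgery is recorded: "demographic data regarding age, gender, body mass index and laterality will be recorded".

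Under Statistical analysis, "Between group comparisons were evaluated with the Mann-Whitney U test", applied to the preoperative and the postoperative measurements. In addition, "Differences between the groups in terms of changes or improvements (post vs. pre) were also assessed with the Mann-Whitney U test". No covariate, regression model, side-to-side comparison or confidence interval is planned. The sample size was set on another outcome, "assuming a minimum difference of 1 point in the VAS value with a standard deviation of 2.5".

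**The concern.** PPT is the trial's only algometric measure of pain at the patella, and anterior knee pain is the primary objective. A patient's threshold at 1 year is likely to be related to the same patient's threshold before surgery. The trial collects that earlier reading. The plan uses it only by subtraction, in the change test, or not at all, in the postoperative test. Neither is the most precise use of a baseline value.

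If the second knee is also measured, its reading has no stated role. General pain sensitivity and the conduct of a session act on both knees, so that reading carries information about the operated knee. A change score cannot remove a session effect specific to the 1-year visit.

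What is at stake is the chance of missing a real local effect on PPT. A rank test alone also gives a p value without an estimated difference and its interval.

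**Working it through.** **Inputs from the documents (Statistical analysis).** 110 per group, difference 1 and SD 2.5 on the VAS, significance level 0.05, power 80%, drop-out 10%. There is no SD, effect size or correlation for PPT.

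**Step 1: the plan's own figure.** n = 2 × (1.960 + 0.842)² × 2.5² / 1² = 98.1, so 99 per group, and 99 / 0.90 = 110. This matches. A one-sided test would need 78, or 87 after drop-out, so the plan's 0.05 is two-sided. I use 99 evaluable per arm below.

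**Step 2: where the error sits.** Split the variance of a single-knee, single-session PPT (set to 1) into P (person), S (session, shared by both knees), K (stable knee-specific) and E (knee-by-session error).

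- 1-year value only: variance P + S + K + E = 1.
- Change from baseline: variance 2(S + E). P and K cancel; S does not.
- Model adjusting for own baseline: variance 1 − r², where r = P + K is the one-year correlation.

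Since 2(S + E) = 2(1 − r), baseline adjustment has a smaller variance than both planned comparisons whenever 0 < r < 1.

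**Step 3: power.** Assumptions: effect 0.3 SD, equal SD at both visits, normal data. Power ≈ Φ(0.3 / √(2V/99) − 1.96) = Φ(2.111/√V − 1.96). At r = 0.5:

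| Analysis | V | Power |
|---|---|---|
| 1-year value, unadjusted | 1 | 56% |
| Change, unadjusted | 2(1 − 0.5) = 1 | 56% |
| Adjusted for own baseline | 1 − 0.25 = 0.75 | 68% |
| Adjusted for both preoperative knees | 1 − 0.27 = 0.73 | 69.5% |

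The last row assumes a between-knee correlation of 0.7 at one visit and 0.45 across knees over a year: R² = (0.5² + 0.45² − 2 × 0.5 × 0.45 × 0.7) / (1 − 0.7²) = 0.1375 / 0.51 = 0.27. The second knee therefore adds about 1 point.

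Simulation under the same assumptions (3,000 runs) gave 54% for Mann-Whitney on the 1-year value, 55% for Mann-Whitney on change, and 70% for each adjusted model.

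**Step 4: range over the assumed one-year correlation.** The 1-year comparison stays at 56% throughout.

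| r | Change | Own-baseline model |
|---|---|---|
| 0.4 | 49% | 63% |
| 0.5 | 56% | 68% |
| 0.6 | 66% | 75% |
| 0.7 | 78% | 84% |

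The gain over the planned change test shrinks as r rises, but does not vanish.

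**Step 5: adding the 1-year contralateral reading.** One-year correlation 0.5; cross-knee correlation over a year in brackets. The side-to-side difference at 1 year has variance 2(1 − between-knee correlation).

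| Between-knee correlation | R², all three covariates | Power as covariate | Power as side-to-side difference |
|---|---|---|---|
| 0.3 (0.2) | 0.29 | 71% | 43% |
| 0.4 (0.3) | 0.32 | 72.5% | 49% |
| 0.6 (0.45) | 0.43 | 80% | 66% |
| 0.7 (0.45) | 0.53 | 87% | 78% |
| 0.8 (0.45) | 0.67 | 96% | 92% |

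As a covariate the reading never hurts in this range. As a difference it falls below the unadjusted 56% once the between-knee correlation is under 0.5.

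**The case against.** The strongest reply is that nothing here is wrong, only less efficient than it could be. Randomisation keeps the planned comparison valid, the sample size rests on the VAS, and anterior knee pain is also scored directly by the patellofemoral score. All of that stands, and it limits the point to precision on one outcome.

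Three stronger readings are tempting, and the documents do not support them.

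- A reader might infer that person-to-person sensitivity stays in the error of every PPT test. It stays in the postoperative comparison. The plan also tests change, where the stable person component cancels; only the session component survives in every planned comparison.
- A reader might infer that the trial ignores an untreated knee that is a clean control. That the second knee is measured is the natural reading of the text, but not an explicit statement. Nor do the documents say that only one knee is operated on: they exclude "patients with a prior major surgery on the same knee", but neither bilateral nor later contralateral arthroplasty. The other knee may be arthritic or replaced by 1 year.
- A reader might infer that both knees would enter the rank test. For between-knee correlations of 0.6-0.8, that would give a null rejection rate of 2 × (1 − Φ(1.96/√(1 + correlation))), or 12-14%. However, the plan randomises and counts patients and never directs pooling, so this is hypothetical. What is missing is one sentence naming the knee.

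It is also fair to say that the large gains in Step 5 need a high between-knee correlation and a covariate measured after randomisation.

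**Conclusion.** The point holds as a loss of precision on PPT, not a bias. The plan collects a baseline PPT and uses it only through subtraction or not at all; any contralateral reading is unused. At an assumed one-year correlation of 0.5 and a 0.3 SD effect, baseline adjustment raises power from about 56% to about 68-70%, nearly all of it from the operated knee's own preoperative value. That part does not depend on whether a second knee was measured.

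The further rise to 71-96% from the 1-year contralateral reading rests on assumed between-knee correlations of 0.3-0.8 and supports no more than an optional supportive analysis. All the power figures rest on assumed correlations and an assumed effect size, because the documents give none for PPT.

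**What to change.** In Data collection and outcome measures, state whether the contralateral knee is measured, and define the PPT outcome as one value per patient: the operated-knee mean of three readings at 1 year.

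In Statistical analysis, compare groups on that value with a linear model adjusting for the operated knee's preoperative PPT, adding the preoperative contralateral PPT where measured. Report the mean difference with its 95% CI.

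Optionally, as a supportive analysis only, add the 1-year contralateral PPT as a covariate, not as a side-to-side difference, and exclude patients whose contralateral knee has a prosthesis.

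The main change costs some wording and one model, on readings already planned. The downside is confined to the optional part. Its covariate is measured after randomisation, so if the release altered general pain sensitivity the contralateral value could shift, and the model would estimate the local effect only. It is also available only if the second knee is in fact measured.

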### Statistical analysis

The sample size calculation of 110 patients in each group was based on assuming a minimum difference of 1 point in the VAS value with a standard deviation of 2.5. A probability level of 0.05, a power of 80% and a drop-out rate of 10% were assumed.

Descriptive statistics were used for the demographic data. Continuous variables and measured scores were presented as mean and standard deviations and categorical variables as number and percentage. Between group comparisons were evaluated with the Mann-Whitney U test. These comparisons were performed with the preoperative and postoperative measurements. Differences between the groups in terms of changes or improvements (post vs. pre) were also assessed with the Mann-Whitney U test.

STATA version 15.1 (StataCorp, College Station, TX, USA) was used for the statistical analysis with p values of 0.05 being considered statistically significant.

For the calculation of intraclass correlation coefficients (ICC) two-way random-effects model approximation was performed, being in terms of *Shrout and Fleiss* notation ICC(2,1) for intrarater agreement and ICC(2,2) for interrater agreement.

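### The trial is sized on an unspecified VAS value, but three VAS conditions are each tested two ways at an unadjusted 0.05, and no primary test is named

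*Combined protocol and SAP*

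**What the plan says.** Under Objectives and hypothesis, the primary objective is the effect of lateral retinacular release (LRR) on anterior knee pain (AKP). Functional and radiological comparisons at 12 months are secondary. The expected result is worded thus: "LRR would decrease the incidence of AKP after TKA with patellar resurfacing". No variable or test is attached to the primary objective.

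Under Data collection and outcome measures, pain is captured preoperatively and at 1 year in several ways. One is "The Visual Analogue Scale (VAS) referred by the patients at rest, when walking and when going up and downstairs". Another is the Feller score ("Patellar pain and function are evaluated with the patellofemoral score"), which gives 15 of its 30 points to AKP intensity. A third is the pressure pain threshold (PPT).

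Under Statistical analysis, the sample size is "based on assuming a minimum difference of 1 point in the VAS value with a standard deviation of 2.5", with a 0.05 level, 80% power and 10% drop-out. Groups are compared by Mann-Whitney on preoperative and postoperative measurements, and then: "Differences between the groups in terms of changes or improvements (post vs. pre) were also assessed with the Mann-Whitney U test". One threshold covers everything, "with p values of 0.05 being considered statistically significant", and no multiplicity adjustment or ordering of outcomes is given.

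**The concern.** A 5% error rate and 80% power are properties of one defined test. Here the only pointer to that test is the sample-size sentence, which refers to VAS in the singular although three VAS ratings are collected. Even if VAS is accepted as the intended primary measure, three conditions in two forms (1-year value and change) leave six tests. Any of them could be reported as the result for the primary objective, and the choice could be made after the data are seen. A reader holding only this plan could not tell.

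Two related gaps widen the choice. The Feller score and PPT also bear on AKP. The hypothesis concerns incidence, yet there is no definition of an AKP case and no comparison of proportions, so the hypothesis as worded has no matching analysis.

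Power is affected too: 80% applies only to the form of VAS that the SD of 2.5 describes, and the plan does not say which form that is.

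**Working it through.** **1. Reproduce the stated sample size.** Inputs from Statistical analysis: difference 1, SD 2.5, alpha 0.05, power 80%, drop-out 10%. Sidedness is not stated.

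n per group = 2 × (1.960 + 0.842)² × 2.5² / 1² = 98.1, so 99 evaluable. Allowing for drop-out, 99 / 0.9 = 110, which matches the plan. A one-sided 0.05 gives 78 evaluable and 87 randomised, which does not match, so the calculation is two-sided. (A t-based calculation gives 100 and 112; the plan's figure comes from the normal approximation.)

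Power with 99 per group: the standardised difference is 1 / (2.5 × √(2/99)) = 2.814, and Φ(2.814 − 1.960) = 80.4%. The arithmetic is sound for one test.

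**2. Count the tests.** Three VAS conditions × two forms = 6. This is a minimum: it leaves out the preoperative comparisons, the Feller score and PPT, and it counts stairs once although up and down might be scored separately.

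**3. False-positive rate with no true effect.** If the six tests were independent, the rate would be 1 − 0.95⁶ = 26.5%. They are not, so correlated standardised group differences were simulated. The between-condition correlation is r and the pre/post correlation within a condition is ρ; across conditions and visits the correlation is rρ. SDs are taken as equal at both visits and the cut-off is ±1.96. The documents give neither correlation; both are assumptions. At ρ = 0.3:

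| Tests available | r | Any p<0.05, either direction | Any p<0.05 favouring LRR (nominal 2.5%) |
|---|---|---|---|
| Six (value and change) | 0.9 | 14% | 7% |
| Six | 0.7 | 19% | 9% |
| Six | 0 (extreme bound) | 24% | 13% |
| Three (1-year value only) | 0.9 | 8% | 4% |
| Three | 0.7 | 11% | 5.5% |
| One VAS, value and change | – | 9% | 4.4% |

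Moving ρ from 0.1 to 0.7 keeps the six-test two-sided rate between 14% and 20% for r from 0.9 to 0.7. Running actual Mann-Whitney tests on rounded 0–10 scores with 99 per group gives much the same: 15%, 19% and 25% at r = 0.9, 0.7 and 0 (ρ = 0.3).

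**4. Power by form of VAS.** Suppose 2.5 is the SD of the 1-year score and SDs are equal at both visits. Then the SD of the change is 2.5 × √(2(1 − ρ)). With 99 per group and a 1-point difference:

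| ρ | SD of change | Power |
|---|---|---|
| 0.1 | 3.35 | 55% |
| 0.3 | 2.96 | 66% |
| 0.5 | 2.50 | 80% |
| 0.7 | 1.94 | 95% |

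**5. If several VAS tests were kept as co-primary with Bonferroni.** Three tests (alpha 0.05/3 = 0.0167): 66% power per test with 99 evaluable, or 131 evaluable and 146 randomised per group to restore 80%. Six tests (alpha 0.05/6 = 0.0083): 57% power, or 152 evaluable and 169 randomised per group.

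**The case against.** Much of the primary analysis can be inferred. The sample size points to VAS, the method is Mann-Whitney, the threshold is 0.05, and 1 year is the only follow-up. The sample-size wording, "a minimum difference of 1 point in the VAS value", reads most naturally as the score itself, and the change analysis is introduced as an addition. That leaves three candidates rather than six. Ratings of one knee at one visit will not be uncorrelated, so the 24% figure is not realistic, and only a result favouring LRR would support the hypothesis. The power range in step 4 arises only if the SD describes the score and change is then made primary; it assumes equal SDs before and after surgery, and power rises above 80% once ρ exceeds 0.5.

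These points narrow the size of the problem. The zero-correlation row should be read only as a bound, and the power figures show ambiguity rather than a shortfall. The omission itself stands: the VAS condition is unnamed on any reading, nothing in the text ranks the value above the change, and no rule combines the three ratings. On the three-test reading the rate is still 8% to 11% two-sided, and 4% to 5.5% favouring LRR against 2.5%. Nor can this be excused as exploratory reporting, because the plan states a primary objective and a hypothesis and reports a power calculation.

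**Conclusion.** The concern holds. The plan does not identify the test that decides its primary objective, so the stated 5% and 80% cannot be tied to a particular analysis. If any VAS result may be taken as the answer, the two-sided false-positive rate is roughly two to four times nominal for between-condition correlations of 0.7 to 0.9: 8% to 11% with three tests, 14% to 20% with six. The omission is certain from the text. Its size depends on assumed correlations and on whether the change is counted. The number randomised is not in dispute. This must be fixed, because the trial's main conclusion rests on the missing choice.

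**What to change.** Before outcomes are compared by allocated group:

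- Name one VAS condition (the sponsor's choice), at 1 year, in one form and with one analysis, as the sole primary test at two-sided 0.05.
- State that the 1-point difference and SD of 2.5 refer to that condition and form.
- Reword the incidence hypothesis to match the chosen measure.
- Make the other VAS conditions, the other form of the chosen VAS, the Feller score and PPT secondary. Either adjust them for multiplicity or report estimates with 95% confidence intervals and no confirmatory claim.

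The analysis text is largely in the past tense and recruitment was planned to end in December 2020, so the analysis may already have been run; the documents do not settle this. If it has, report all six VAS tests together and state that the primary was not pre-specified.

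The cost is a few lines in the statistical section. With one primary test the 110 per group stands and no extra data are needed. The sponsor gives up a primary claim on the other pain measures.

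### Two unadjusted Mann-Whitney tests per score (12-month value and change), with neither named as deciding, no between-group difference with a confidence interval, and baseline not used as a covariate

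*Combined protocol and SAP*

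**What the plan says.** Under Data collection and outcome measures, the scores are taken twice: "At the preoperative visit and at the 1-year follow up, the following clinical and radiological data will be collected". VAS has several items: "The Visual Analogue Scale (VAS) referred by the patients at rest, when walking and when going up and downstairs".

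Under Statistical analysis, the between-group test is Mann-Whitney, and "These comparisons were performed with the preoperative and postoperative measurements". A further test is then added: "Differences between the groups in terms of changes or improvements (post vs. pre) were also assessed with the Mann-Whitney U test". The only decision rule is a p value of 0.05. Results are summarised by group: "Continuous variables and measured scores were presented as mean and standard deviations". The section mentions no between-group effect estimate, confidence interval or covariate.

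The sample size rests on "assuming a minimum difference of 1 point in the VAS value with a standard deviation of 2.5", and "A probability level of 0.05, a power of 80% and a drop-out rate of 10% were assumed".

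**The concern.** Each score gets two outcome tests that answer related but different questions, and the plan does not say which to believe if they disagree. The sample size statement does not settle this. It does not say which VAS item carries the 1-point difference, or whether 2.5 is the SD of the 12-month value or of the change. It gives no pre/post correlation. The power of each planned test depends on those facts.

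The trial was sized on a 1-point mean difference, but the planned output is group means, SDs and rank-test p values. After a non-significant result, the report would not say whether a 1-point benefit has been excluded unless readers worked it out themselves.

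The preoperative value enters only through the change score and through a between-group test at baseline. That baseline test checks a null hypothesis that randomisation already makes true.

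**Working it through.** **Inputs from the Statistical analysis section.** Difference 1 point, SD 2.5, alpha 0.05 (taken as two-sided), power 80%, drop-out 10%, 110 per group.

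**Assumptions.** The correlation rho between preoperative and 12-month scores is not in the documents, so 0.1, 0.3, 0.5 and 0.7 are tried. The main calculation assumes normal data with equal SDs at the two visits.

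**The plan's own figure.** n = 2 × (1.960 + 0.842)² × 2.5² / 1² = 98.1, so 99 per group, and 99 / 0.9 = 110. It reproduces exactly. It does so whichever quantity has SD 2.5, so it cannot show which test was powered.

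**Two readings of 2.5.**

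- (A) 2.5 is the SD at each visit. SD of change = 2.5 × √(2(1 − rho)) = 3.35, 2.96, 2.50, 1.94. ANCOVA residual SD = 2.5 × √(1 − rho²) = 2.49, 2.38, 2.17, 1.79.
- (B) 2.5 is the SD of the change. SD at each visit = 2.5 / √(2(1 − rho)) = 1.86, 2.11, 2.50, 3.23. ANCOVA residual SD = 2.5 × √((1 + rho)/2) = 1.85, 2.02, 2.17, 2.30.

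For rho between 0 and 1, neither ANCOVA SD exceeds 2.5. Its power therefore stays at about 80% or more without knowing rho.

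**Power for a 1-point difference, 99 per arm** (Mann-Whitney by simulation, 10,000 replicates per cell; ANCOVA from the noncentral t):

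| Reading | Analysis | rho 0.1 | 0.3 | 0.5 | 0.7 |
|---|---|---|---|---|---|
| A | Mann-Whitney, 12 months | 77% | 78% | 78% | 78% |
| A | Mann-Whitney, change | 52% | 64% | 78% | 94% |
| A | ANCOVA | 80% | 84% | 90% | 97% |
| B | Mann-Whitney, 12 months | 96% | 89% | 78% | 56% |
| B | Mann-Whitney, change | 78% | 77% | 78% | 78% |
| B | ANCOVA | 96% | 93% | 90% | 86% |

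**Where the two planned tests cross.** Change has the smaller variance when rho exceeds SD_pre / (2 × SD_post), which is 0.5 with equal SDs. With a 12-month SD of 2.5, an assumed preoperative SD of 2.0 moves this to 0.4 (change power 73% at rho 0.3 and 84% at 0.5). An assumed 3.0 moves it to 0.6 (55% and 70%).

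**Disagreement.** With a true 1-point effect, the two planned tests differ on significance in about 33%, 29%, 24% and 23% of trials under (A), and about 20%, 20%, 24% and 37% under (B).

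**Precision under (A).** The 95% half-width is 1.972 × SD × √(2/99). This gives 0.70 points for the 12-month value; 0.94, 0.83, 0.70, 0.54 for change; and 0.70, 0.67, 0.61, 0.50 for ANCOVA.

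**Floor-heavy data.** A further simulation (4,000 replicates) clipped VAS to 0–10. It assumed a control SD of 2.5 with mean 2.5 or 3.0, a release mean 1 point lower, and a preoperative mean of 6 with SD 2. Zeros were 28% against 46%, or 18% against 32%. ANCOVA used robust (HC3) standard errors.

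| Analysis | observed rho about 0.1 | 0.3 | 0.5 | 0.65 |
|---|---|---|---|---|
| Mann-Whitney, 12 months | 85–88% | 85–88% | 85–88% | 85–88% |
| Mann-Whitney, change | 65% | 74–75% | 85% | 95–97% |
| ANCOVA | 84–87% | 87–88% | 92–93% | 98% |

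ANCOVA's type I error was 4.4–5.5%. Compared setting by setting, its power ran from about 1 point below to 2 points above the 12-month Mann-Whitney at correlations of 0.1 to 0.3, and 5 to 11 points above at 0.5 to 0.65.

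**The case against.** The strongest reply is that a rank test is a legitimate choice for a bounded, skewed pain score, and that the efficiency argument rests on a correlation the documents do not give. At low correlation on floor-heavy data, ANCOVA may gain nothing over the 12-month Mann-Whitney. That stands, and it makes covariate adjustment the recommended option rather than the core of the point. It does not excuse two unranked tests or the missing interval.

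The sizing statement speaks of a VAS value and not of a change, which leans towards reading (A). The 12-month test then keeps about 78% power. That is a fair inference but not a statement in the plan, and the plan still does not make that test decide.

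Some disagreement between analyses is normal. Under (A), ANCOVA and the 12-month Mann-Whitney would themselves disagree in about 6%, 10%, 14% and 19% of trials. The defect is the missing hierarchy, not disagreement as such. Likewise, a type I error of about 9% for one score arises only if success on either test were counted, which the plan does not say, so it adds no weight here.

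An approximate unadjusted interval can be derived from the reported means and SDs. This softens the gap but leaves the key result for readers to construct. The baseline p values are a minor matter.

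Finally, the stated hypothesis concerns the incidence of anterior knee pain, so VAS as primary is inferred from the sample size. If incidence were made primary, a linear model of VAS would not be the deciding analysis. That choice of endpoint is a separate question. The present point applies to VAS as the outcome the trial was sized on, and to the other scores analysed the same way.

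**Conclusion.** The concern holds. Four facts follow from the text alone: two unadjusted tests per score, no deciding test, no between-group difference with a confidence interval, and a collected baseline that is not used as a covariate.

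The size of the consequence depends on the assumed correlation and, for the main figures, on normality and equal SDs. Across correlations of 0.1 to 0.7, one of the two planned tests can fall to about 52% power (change, reading A) or 56% (12-month value, reading B), against the planned 80%. ANCOVA does not fall materially below 80% on normal data under either reading. The plan should be changed on this point, but the trial is not invalid as it stands, because a valid 12-month test is among those planned.

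**What to change.** - Name one VAS item at 12 months as the outcome that carries the 1-point target. State whether 2.5 is the SD of the 12-month value or of the change.
- Make one analysis decide: linear regression of the 12-month score on randomised group and its preoperative value, with robust standard errors. Report the adjusted mean difference and 95% CI against 1 point.
- Keep Mann-Whitney on the 12-month value as a sensitivity analysis. Make the change-score test descriptive or drop it, and drop the baseline p values.
- Adjustment for surgeon is optional. Rank methods may stay for the 5-point components of the patellofemoral score.
- If the team prefers a rank test as primary, name the 12-month Mann-Whitney as deciding and add a Hodges-Lehmann difference with 95% CI. This closes the reporting gap but not the efficiency gap.
- The section is written in the past tense. If results by arm have already been seen, label the regression post hoc and show it beside the planned tests.

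The cost is SAP wording and one regression per outcome on data already collected, using one extra degree of freedom from about 198 patients (2 × 99). The downside is that adjustment may gain nothing on floor-heavy data with a low correlation.
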